## 1.0 TRIAL SUMMARY

[figure not shown]
Abbreviated Title	Pembrolizumab for MRD in Adults with ALL
Trial Phase	II
Clinical Indication	Acute lymphoblastic leukemia/lymphoma
Trial Type	Single-arm, non-randomized
Type of control	None
Route of administration	Intravenous
Trial Blinding	None
Treatment Groups	1
Number of trial subjects	21
Estimated enrollment period	6/1/2016 – 10/1/2018
Estimated duration of trial	3 years
Duration of Participation	Up to 2 years

## 2.0 TRIAL DESIGN

### 2.1 Trial Design

This is a single-institution, non-randomized, prospective, phase II trial of pembrolizumab (MK-3475) in adult patients with acute lymphoblastic leukemia (ALL) with minimal residual disease (MRD), as defined by a bone marrow examination consistent with morphologic complete remission (i.e., less than 5% blasts) and no clinically-apparent extramedullary disease but quantifiable molecular or immunophenotypic evidence of disease by either polymerase chain reaction (PCR) or multiparameter flow cytometry (MFC), respectively.

### 2.2 Trial Diagram

\* Subsequent cycles will be administered in the absence of morphologic relapse/progression or development of extramedullary disease (as defined in Section 7.1.2.6) or transition to alternative therapy at the discretion of the patient and treating investigator.

^. Long-term follow-up will occur for up to 2 years after completion of treatment or until relapse to determine duration of complete MRD response and overall survival.

9458- Protocol Version Date 28 Feb 2019

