disease status until disease progression, initiating a non-study cancer treatment, withdrawing consent or becoming lost to follow-up. After documented disease progression each subject will be followed by medical record review and/or telephone for overall survival until death, withdrawal of consent, or the end of the study, whichever occurs first.

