### **7.1.2.6 Assessment of Disease**

Bone marrow examinations will be the primary modality for disease assessments on this study. The bone marrow performed for screening/eligibility may be performed at an outside

9458- Protocol Version Date 28 Feb 2019

institution, provided an assessment of morphology was performed that confirmed morphologic CR and MRD was detected by either MFC or PCR. If the marrow exam was performed > 28 days before the start of treatment or if either of these elements is not available, a repeat bone marrow exam will be required prior to enrollment.

Following the initiation of treatment, bone marrow exams will be repeated after each of the first 2 cycles of treatment. These should be performed  $3 \pm 1$  days prior to the start of the subsequent cycle (i.e., Day 18-20) to provide adequate time for interpretation. At a minimum, bone marrow exams will include an evaluation of morphology as well as a repeat analysis of whatever study (or studies) detected MRD at the time of enrollment (e.g., if MRD was detected by MFC and PCR at enrollment, follow-up marrow exams should include both MFC and PCR); other studies may be included as clinically indicated.

If morphologic relapse (i.e., leukemic blasts in the peripheral blood or  $\geq 5\%$  blasts in the bone marrow not attributable to any other cause) is detected at any time, treatment will stop and the subject will be removed from the study. However, subjects with persistent MRD may continue, provided other criteria to continue study treatment are met.

As our institution's standard methods for MRD detection in ALL are either MFC or PCR for the *BCR-ABL* fusion product in patients that have Ph+ disease, it is anticipated that these will be the primary modalities by which MRD is monitored. That said, for patients from whom adequate baseline material is available, NGS performed in the UW Hematopathology Laboratory or at Adaptive Biotechnologies will be used as an additional method of MRD monitoring. These results, however, will not be available in real time, and thus clinical decision-making will rest entirely on the results of MFC and/or PCR.

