For subjects who are eligible to proceed to Cycles 3 and beyond, bone marrow exams will be repeated after every other cycle (i.e., Cycle 4, 6, and 8) through Cycle 8. For those eligible to continue beyond Cycle 8, the timing of subsequent bone marrow exams will be left to the treating investigator, though every 3 months while receiving study treatment will be recommended.

A bone marrow exam will also be required at the end of treatment. If the decision to discontinue treatment coincides with the timing of one of the above follow-up assessments, a separate end-of-treatment examination will not be required (e.g., the post-cycle 4 bone marrow demonstrated morphologic relapse). Similarly, if morphologic relapse is detected after Cycle 1, no further bone marrow examinations will be required for this study.

For definitions of response categories, please see Section 12.3.

Imaging studies will only be performed if extramedullary disease is suspected based on the evaluation of the treating investigator. This may occur at screening (to ensure eligibility) or at end of treatment (to document relapse/progression). If extramedullary disease is identified, this will constitute disease relapse: study treatment will be discontinued, and the subject will be removed from the study.

9458- Protocol Version Date 28 Feb 2019

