#### **7.1.5.3.2 Follow-up Visits**

Subjects who discontinue trial treatment for a reason other than disease progression will move into the Follow-Up Phase and should be assessed approximately every 3 months for up to 2 years. These assessments may be performed by local or referring medical providers, provided appropriate medical records can be made available to research staff. Every effort should be made to collect information regarding disease status until the start of new anti-neoplastic therapy, disease progression, death, end of the study or if the subject begins retreatment with pembrolizumab as detailed in Section 7.1.5.5. Information regarding post-study anti-neoplastic treatment will be collected if new treatment is initiated. If this anti-neoplastic treatment includes allogeneic HCT, occurrence of graft rejection and/or grade 3 or higher acute GVHD according to section 12.4 will be noted.

Subjects who are eligible to receive retreatment with pembrolizumab according to the criteria in Section 7.1.5.5 will move from the follow-up phase to the Second Course Phase when they experience disease progression. Details are provided in Section 6.1 – Trial Flow Chart (i.e., Second Course Phase will be identical to initial treatment).

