#### **7.1.5.3.3 Survival Follow-up**

Once a subject experiences confirmed disease progression or starts a new anti-cancer therapy, the subject moves into the survival follow-up phase and should be contacted (via medical record review and/or telephone) approximately every 3 months to assess for survival status until death, withdrawal of consent, or the end of the study, whichever occurs first.

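### The protocol contradicts itself on survival follow-up after relapse, and it does not give all subjects one survival horizon

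*Combined protocol and SAP*

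**What the plan says.** **After relapse, follow-up ends.** The note to the diagram in Section 2.2 sets long-term follow-up "for up to 2 years after completion of treatment or until relapse to determine duration of complete MRD response and overall survival". Section 7.1.2.6 says that at morphologic relapse "treatment will stop and the subject will be removed from the study", and at extramedullary relapse "study treatment will be discontinued, and the subject will be removed from the study". Section 5.8 lists relapse among the reasons for discontinuing a subject from the trial as a whole.

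**After relapse, follow-up continues.** Section 5.8 goes on: "After documented disease progression each subject will be followed by medical record review and/or telephone for overall survival until death", or until withdrawal of consent or study end. Section 7.1.5.3.3 covers confirmed progression or new anti-cancer therapy: "the subject moves into the survival follow-up phase and should be contacted (via medical record review and/or telephone) approximately every 3 months", again "to assess for survival status until death, withdrawal of consent, or the end of the study". The flow chart in 6.1 has a survival follow-up column.

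**Without relapse.** Under 7.1.5.3.2, subjects who stop treatment for a reason other than progression "should be assessed approximately every 3 months for up to 2 years". Section 5.8 follows the same subjects for disease status with no 2-year limit. Section 1.0 gives participation of up to 2 years, although 5.8 allows initial treatment alone to run 24 months or 35 doses, whichever is later.

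**Use of OS.** Section 3.2 makes the link from MRD response to relapse-free and overall survival a secondary objective. Section 9.2 calls the reporting of OS primarily descriptive and gives no censoring rule.

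**The concern.** Follow-up that ends at relapse cannot determine OS, because the deaths after relapse are not observed. Censoring there is informative: a subject who has just relapsed has a worse outlook than those still at risk. Section 4.2.1 says MRD almost always leads to relapse without further intervention, so many subjects could be affected. The hypothesis in 3.2 is that complete MRD responders live longer. If non-responders relapse more often, as expected, lost deaths would be concentrated among them and the comparison would be blurred.

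The second issue is unequal follow-up length. If subjects without relapse stop contributing at a fixed point while relapsed or re-treated subjects continue, the late part of the OS curve rests too heavily on the group with the poorer outlook.

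No section says which rule takes precedence, and survival status that was not collected may be hard to recover.

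**Working it through.** The plan states no OS figure to reproduce. The check is a comparison of the rules, then an illustration of what each would do to a Kaplan-Meier estimate.

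**1. Rules side by side**

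| Subject | Follow-up ends early | Follow-up continues |
|---|---|---|
| Relapsed | 2.2 (at relapse); 7.1.2.6 (out of the study) | 5.8, 7.1.5.3.3, flow chart 6.1 (no cap) |
| New therapy, no relapse | 2.2 (2 years after treatment) | 7.1.5.3.3 (no cap) |
| Neither | 2.2 and 7.1.5.3.2 (2 years after treatment) | 5.8 (no cap stated) |

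**2. Effect of censoring at relapse**

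Assumed inputs, none from the documents: constant hazards, with median time to relapse 6, 12 or 24 months, median survival after relapse 4 to 12 months, and median time to death without relapse 60 or 120 months. Each hazard is ln 2 divided by its median: *a* for relapse, *b* for death after relapse, *d* for death without relapse.

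True OS: S(t) = exp(−(a+d)t) + [a/(a+d−b)] × [exp(−bt) − exp(−(a+d)t)].

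Kaplan-Meier censored at relapse estimates exp(−dt). At 24 months this is 2^(−24/60) = 0.758 or 2^(−24/120) = 0.871, whatever the relapse hazard or survival after relapse.

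| Median relapse / death after relapse (months) | True 24-month OS, d median 60 / 120 | Overstatement, points |
|---|---|---|
| 6 / 4 | 0.127 / 0.141 | 63 / 73 |
| 6 / 8 | 0.269 / 0.290 | 49 / 58 |
| 12 / 6 | 0.348 / 0.390 | 41 / 48 |
| 12 / 12 | 0.492 / 0.541 | 27 / 33 |
| 24 / 12 | 0.594 / 0.667 | 16 / 20 |

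Worked case, 12 / 12 / 60: a = b = 0.0578 and d = 0.0116, so a+d = 0.0693. S(24) = 0.1895 + 5 × (0.2500 − 0.1895) = 0.492. The gap is 0.758 − 0.492 = 0.266.

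A second set of assumptions takes medians of 6 or 12 months for relapse and for survival after it, with 0.5% per month death without relapse. It gives true 24-month OS of 22% to 55%, against exp(−0.005 × 24) = 0.887 when censored at relapse.

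**3. Effect of the 2-year cap alone**

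Here relapsed subjects are followed on, and the others are censored at treatment end plus 24 months. Treatment was assumed to last 3, 6 or 12 months unless relapse or death came first. Simulation with 400,000 subjects per scenario gave:

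- 12 and 24 months: no difference from true OS.
- 30 months: OS understated by 0.2 to 0.8 points.
- 36 months: OS understated by about 0.5 points (0.108 true against 0.103) to about 4 points (0.490 against 0.448).

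The cap cannot act before 24 months on the OS clock, because it starts when treatment ends. The two problems act in opposite directions.

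**4. Effect of the repair**

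With every subject followed to death or a common study end, regardless of relapse, the simulated Kaplan-Meier estimate stayed within about 0.3 points of true OS in every scenario.

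**The case against.** The strongest reply is that Sections 5.8 and 7.1.5.3.3 are the operative follow-up text. They are specific, the flow chart agrees with them, and the data-management text (11.5 and the paragraph numbered 12.0 after it) lists follow-up for relapse and survival among the data to collect. Against them stands a note to a diagram, whose stop at relapse fits the first quantity it names, the duration of MRD response. Section 5.8 also speaks of discontinuing relapsed subjects from the trial and then requires survival follow-up for them. Leaving the study need not end survival contact in this protocol's usage.

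Most of this stands. A reader might infer that OS will be biased simply because the protocol is followed. The documents do not support that: the large bias needs the 2.2 and 7.1.2.6 wording to override 5.8, 7.1.5.3.3 and the flow chart. A reader might also infer that subjects without relapse are followed for only 2 years in all, so that the OS risk set after year 2 is mainly relapsed or re-treated subjects. That is not supported either. The 2 years run from the end of treatment, 5.8 states no cap, and subjects who start new therapy move to uncapped follow-up. With an estimated trial duration of 3 years, few subjects would reach the affected range.

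What the reply does not remove is the contradiction. No section ranks the rules, 7.1.2.6 names stopping treatment and removal from the study as two separate acts, and 9.2 has no censoring rule to settle it. Descriptive reporting does not make informative censoring harmless.

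**Conclusion.** The contradiction on survival follow-up after relapse is real and should be reconciled. Its effect is conditional. Under 2.2 and 7.1.2.6, 24-month OS would be overstated by about 16 to 73 points across the assumed hazards, and by more than 25 points in eight of the ten scenarios. Under 5.8 and 7.1.5.3.3, this bias is absent. The unequal horizon in 7.1.5.3.2 is a lesser, separate matter: no effect through 24 months, then a downward bias of about 0.5 to 4 points at 36 months on assumed inputs. All these sizes rest on constant hazards and medians chosen for illustration. The contradiction itself rests on the text alone. The primary endpoint and the early-relapse stopping rule are unaffected; OS is secondary and descriptive, in a trial of 21 subjects.

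**What to change.** - **2.2:** state that disease-status follow-up runs until relapse, to measure duration of complete MRD response, and that survival follow-up continues after relapse under 7.1.5.3.3.
- **5.8 and 7.1.2.6:** where relapse is the reason, replace the wording about leaving the trial or study with *discontinued from study treatment and moved to survival follow-up (7.1.5.3.3)*. This separates off treatment from off study and does not change when treatment stops.
- **7.1.5.3.2:** continue 3-monthly survival contact for every subject, relapsed or not, to the same end of study. Define that end, and reconcile the 2-year limits in 1.0, 2.2 and 7.1.5.3.2 with 5.8.
- **9.2:** state that OS is censored only at the date last known alive or the common data cutoff, never at relapse.

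The cost is protocol wording plus a few extra telephone or record contacts for subjects without relapse, by the means 7.1.5.3.3 already provides.

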### 3.0 OBJECTIVES & HYPOTHESES

#### 3.1 Primary Objective & Hypothesis

- (1) **Objective:** To evaluate the efficacy of pembrolizumab in MRD-positive ALL.

**Hypothesis:** Pembrolizumab will yield a complete MRD response rate of  $\geq 50\%$ .

#### 3.2 Secondary Objectives & Hypotheses

- (1) **Objective:** To describe the toxicity profile of pembrolizumab in patients with previously-treated ALL.

**Hypothesis:** Pembrolizumab will be safe and well-tolerated in this patient population.

- (2) **Objective:** To gain a preliminary assessment of how MRD response translates into relapse-free and overall survival.

**Hypothesis:** Patients that experience a complete MRD response will have longer morphologic relapse-free and overall survival than those who do not.

#### 3.3 Exploratory Objectives

- (1) **Objective:** To compare disease assessments by MFC and PCR to a newly-developed and more sensitive next generation sequencing (NGS)-based platform.

**Hypothesis:** NGS will be able to detect MRD in a subset of patients that appear to have complete MRD response by MFC and/or PCR, and subsequent relapse will occur more frequently in these patients.

- (2) **Objective:** To correlate response to pembrolizumab to immunologic markers in peripheral blood and bone marrow specimens.

**Hypotheses:** Patterns of changes in peripheral blood mononuclear cells (PBMC) and circulating cytokines will emerge as predictors of an immunologic response and anti-leukemia efficacy.

- (3) **Objective:** To evaluate if treatment with pembrolizumab has a measurable impact on hematopoietic engraftment and graft-vs-host disease (GVHD) in patients who subsequently undergo allogeneic hematopoietic cell transplantation (HCT).

**Hypothesis:** Prior treatment with pembrolizumab will not increase the risk of graft rejection or acute GVHD (compared to historical data) in those patients that subsequently undergo HCT.

9458- Protocol Version Date 28 Feb 2019

## 4.0 BACKGROUND & RATIONALE

### 4.1 Background

Refer to the Investigator's Brochure (IB)/approved labeling for detailed background information on MK-3475.

#### 4.1.1 Pharmaceutical and Therapeutic Background

The importance of intact immune surveillance in controlling outgrowth of neoplastic transformation has been known for decades. Accumulating evidence shows a correlation between tumor-infiltrating lymphocytes (TILs) in cancer tissue and favorable prognosis in various malignancies. In particular, the presence of CD8+ T-cells and the ratio of CD8+ effector T-cells / FoxP3+ regulatory T-cells seems to correlate with improved prognosis and long-term survival in many solid tumors.

The PD-1 receptor-ligand interaction is a major pathway hijacked by tumors to suppress immune control. The normal function of PD-1, expressed on the cell surface of activated T-cells under healthy conditions, is to down-modulate unwanted or excessive immune responses, including autoimmune reactions. PD-1 (encoded by the gene *Pdcd1*) is an Ig superfamily member related to CD28 and CTLA-4 which has been shown to negatively regulate antigen receptor signaling upon engagement of its ligands (PD-L1 and/or PD-L2). The structure of murine PD-1 has been resolved. PD-1 and family members are type I transmembrane glycoproteins containing an Ig Variable-type (V-type) domain responsible for ligand binding and a cytoplasmic tail which is responsible for the binding of signaling molecules. The cytoplasmic tail of PD-1 contains 2 tyrosine-based signaling motifs, an immunoreceptor tyrosine-based inhibition motif (ITIM) and an immunoreceptor tyrosine-based switch motif (ITSM). Following T-cell stimulation, PD-1 recruits the tyrosine phosphatases SHP-1 and SHP-2 to the ITSM motif within its cytoplasmic tail, leading to the dephosphorylation of effector molecules such as CD3 $\zeta$ , PKC $\theta$  and ZAP70 which are involved in the CD3 T-cell signaling cascade. The mechanism by which PD-1 down modulates T-cell responses is similar to, but distinct from that of CTLA-4 as both molecules regulate an overlapping set of signaling proteins. PD-1 was shown to be expressed on activated lymphocytes including peripheral CD4+ and CD8+ T-cells, B-cells, T regs and Natural Killer cells. Expression has also been shown during thymic development on CD4-CD8- (double negative) T-cells as well as subsets of macrophages and dendritic cells. The ligands for PD-1 (PD-L1 and PD-L2) are constitutively expressed or can be induced in a variety of cell types, including non-hematopoietic tissues as well as in various tumors. Both ligands are type I transmembrane receptors containing both IgV- and IgC-like domains in the extracellular region and contain short cytoplasmic regions with no known signaling motifs. Binding of either PD-1 ligand to PD-1 inhibits T-cell activation triggered through the T-cell receptor. PD-L1 is expressed at low levels on various non-hematopoietic tissues, most notably on vascular endothelium, whereas PD-L2 protein is only detectably expressed on antigen-presenting cells found in lymphoid tissue or chronic inflammatory environments. PD-L2 is thought to control immune T-cell activation in lymphoid organs, whereas PD-L1 serves to dampen unwarranted T-cell function in peripheral tissues. Although healthy organs express little (if any) PD-L1, a variety of cancers were demonstrated to express abundant levels of this T-cell inhibitor. PD-1 has been suggested to regulate tumor-specific T-cell expansion in subjects with melanoma

9458- Protocol Version Date 28 Feb 2019

(MEL). This suggests that the PD-1/PD-L1 pathway plays a critical role in tumor immune evasion and should be considered as an attractive target for therapeutic intervention.

Pembrolizumab is a potent and highly selective humanized monoclonal antibody (mAb) of the IgG4/kappa isotype designed to directly block the interaction between PD-1 and its ligands, PD-L1 and PD-L2. Keytruda™ (pembrolizumab) has recently been approved in the United States for the treatment of patients with unresectable or metastatic melanoma and disease progression following ipilimumab and, if BRAF V600 mutation positive, a BRAF inhibitor.

#### **4.1.2 Preclinical and Clinical Trial Data**

Refer to the Investigator's Brochure for Preclinical and Clinical data.

### **4.2 Rationale**

#### **4.2.1 Rationale for the Trial and Selected Subject Population**

ALL is among the most common forms of cancer in children, and in this circumstance it is highly curable. However, treatment of ALL in adults is very challenging, and outcomes with standard approaches remain unsatisfactory. Apart from the use of ABL kinase inhibitors for patients with the Philadelphia chromosome (t[9;22], abbreviated Ph+), the treatment still relies primarily upon remission induction with intensive multiagent cytotoxic chemotherapy. This is a particular challenge in older adults diagnosed with ALL, as these regimens are (in general) prohibitively toxic for these patients. Therefore, improvements in the treatment of ALL in adults are critically needed.

The importance of MRD in ALL is firmly established. MRD is typically assessed by two different techniques: multiparameter flow cytometry (MFC) to detect the unique abnormal immunophenotype of the leukemic blasts, or polymerase chain reaction (PCR) for clonal DNA alterations (including immunoglobulin or T-cell receptor gene rearrangements or oncogenic chromosomal rearrangements like BCR-ABL). It is understood that the presence of MRD (either as persistence during therapy or reappearance afterward) confers a poor prognosis, as it almost inevitably heralds frank hematologic relapse without additional intervention. Our center's experience also demonstrates the risk associated with MRD in the context of HCT. Its presence is associated with a significantly higher risk of relapse when detected before or after myeloablative HCT. Qualitatively comparable results have been observed from patients undergoing nonmyeloablative conditioning, which may be the only option for HCT in older or medically-infirm patients ([name], personal communication). Unfortunately, for those that have MRD, little is known about the optimal management of this high-risk scenario. However, it stands to reason that elimination of MRD could significantly improve their outcome.

